Data from literature suggests that pilot studies that aim to inform larger trials should include \geq 30 participants to estimate a parameter (16). Based on this, 30 patients will be included in each arm of the trial (total: n=60).

Recruitment

Eligible COPD patients, attending the Chapidze Emergency Cardiology Center, will be invited to take part in the feasibility trial. Those who work in the clinic (e.g. respiratory consultant, or consultant's assistant) will either phone existing clinic patients to provide information about the study, or inform those who are attending their clinic appointment. To encourage recruitment of a range of socioeconomic groups, patients will be recruited from primary care and other hospitals within Tbilisi.

Patients who are interested will be provided with the study invitation documents (including participant information sheet and reply slip) via email or post (through the DHL service, as the national postal service is unreliable). These documents will be provided at the time of the clinic appointment, for those who indicate an interest in-person.

Methods: Data collection, management, and analysis

Data collection methods

Phase 1: Tailoring pulmonary rehabilitation to the Georgian context

Three focus group discussions will be carried out, lasting up to 2 hours each, and will be audio-recorded. Informed consent will be gained at the time of the focus group session. No other research visits will be involved in the phase of the study.

Phase 2: Randomised controlled feasibility trial

Study assessment 1

The baseline research assessment is likely to last approximately 90 - 120 minutes, and include the following components:

Eligibility check: this will be assessed based on the inclusion/exclusion criteria above.
 Spirometry will be carried out by the respiratory team at the Chapidze clinic, who will confirm COPD diagnosis.

- 2. Informed consent: Participants will have the opportunity to ask any questions before completing the consent form with the researcher. As well as consenting to the main study, participants will asked to consent to being contacted and take part in the qualitative interviews linked to this study.
- 3. Completion of the case report form (CRF), which will include the following:
 - a. Documenting patient details (initials, age, sex, ethnicity and employment status)

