 - b. Conducting the Incremental Shuttle Walking Test (ISWT): to be carried out twice; distance walked to be documented in meters; collect various measures pre and post each test (blood pressure, heart rate, oxygen saturations, Borg dyspnoea and RPE scores); record reason for cessation (e.g. breathless, dizziness, painful legs).
 - c. Self-administered participant questionnaire booklet: sociodemographic data (age, sex, ethnicity, education level, marital status, number of dependents; number of adults in the household; and employment); comorbidities; medications; level of dyspnoea (MRC score); smoking status; quality of life and disease specific questionnaires (EQ-5D-5L; St George's Respiratory Questionnaire [SGRQ]; and COPD Assessment Test [CAT]); anxiety and depression (GAD 7 and PHQ-9); self-reported physical activity levels (International Physical Activity Questionnaire [IPAQ]); and health service use (hospitalisations).
 - d. Measuring height and weight to calculate body mass index (BMI)
 - e. Saliva or urine sample to measure cotinine (nicotine levels)
- 4. Randomisation to the treatment or control group

The baseline assessment will be carried out by a member of the research team (exception: the ISWT will be carried out by the trained rehabilitation specialist(s)). The researcher will record all study data on CRFs to ensure standardised data collection/recording. On completion, the researcher will enter the data on to the secure REDcap electronic database.

Study assessment 2

At the end of the PR programme, participants will be invited to a second study assessment. This will include collecting similar data as the baseline assessment:

- 1. Conducting the ISWT (once), and collecting all pre and post-test measures (as detailed above), by the rehabilitation specialist
- 2. Self-administered participant questionnaire including the following: level of dyspnoea (MRC score); smoking status; quality of life and disease specific questionnaires (EQ-5D-5L; St George's Respiratory Questionnaire [SGRQ]; and COPD Assessment Test [CAT]); anxiety and depression (GAD 7 and PHQ-9); self-reported physical activity levels (International Physical Activity Questionnaire [IPAQ]); health service use (hospitalisations); patients costs (for those attending the PR programme); and injuries or health issues as a result of the PR programme.
- 3. Saliva or urine sample to measure cotinine (nicotine levels)

Study assessment 3

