We will report recruitment and follow-up rates, with 95% confidence intervals, as a measure of feasibility of the trial. Although the trial will not be powered to detect a difference between intervention and wait-list control, we will calculate the HRQoL at PR end and 6 months for those allocated to each group; 95% confidence intervals will be provided for estimates obtained. The economic analysis will report questionnaire completion rates, and a cost-consequences analysis. This will include a descriptive analysis of health care costs and EQ-5D-5L scores and an initial estimate of the cost of PR, taking into account the duration of the intervention, format of sessions and number of sessions attended by each participant.

Qualitative data

The Framework approach to data management and analysis will be used for the interviews and focus groups (17).

Methods: Monitoring

Data monitoring

The study will be overseen by a Study Steering Committee, consisting of one representative from each of the following stakeholder groups: patient, clinician/policy maker, research team and, the Breathe Well executive committee. In addition there will be two representatives from the International Scientific Advisory Committee, one of whom will act as chairperson. The Study Steering Committee will meet on a 6-12 monthly basis, as required.

The research team will hold monthly meeting with the Breathe Well executive committee, to discuss current progress and any issues arising.

Harms

The focus group discussions, physiological and questionnaire-based measures pose no risk to the participants.

Non-serious adverse events

The risk of harm associated with study procedures and the intervention are considered to be very low. To further minimise the risk of events, we will:

- 1. Ensure patients meet the eligibility criteria
- 2. Carry out a risk assessment (e.g. of the venue, risks to patients and staff) see appendix 2
- 3. Staff will be trained to manage any risks that are identified in the assessment

Due to the low risk in this study, only the following non-serious adverse events will be collected which will form part of the study outcomes:

- Musculoskeletal injury as a result of the intervention
- Other minor injuries as a result of the intervention
- Non-serious medical events during the rehabilitation that do not require admission to hospital, e.g. participant had to stop due to angina attack that resolved with medication.

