Data on these occurrences will be collected on the participant CRF, and documented on an incident log (appendix 3) during each session. This information will be periodically assessed a member of the research team to identify any further training needs for the rehabilitation specialists.

Patients who are identified to have any suicidal thoughts (according to the PHQ-9 questionnaire at baseline) will be managed according to standard clinical practice in Georgia e.g. referral to a psychologist or primary care doctor.

Serious adverse events

Serious adverse events (SAEs) will be defined as an untoward medical occurrence that results in death, is life-threatening, requires hospitalisation, results in persistent or significant disability or incapacity, or is considered medically significant by the study investigator.

There are some potential SAEs which could be expected to occur during the exercise components of the PR programme, although assessing the eligibility of the participants according to the exclusion criteria will minimise this risk e.g. people with unstable cardiovascular disease, musculoskeletal or neurological conditions the prevent exercise and those with very poor balance.

We do not anticipate SAEs to occur in this study, but this is a group of patients with comorbidities doing an exercise intervention. With suitable monitoring by the rehabilitation specialists, we would expect SAEs to be minimised. But if they do occur, all SAEs will be recorded in the CRF and the database. SAEs will be reported to the chief investigator immediately and within 2 working days of being made aware of the event. If, in the opinion of the local doctor or chief investigator, the event was: 'related' (resulted from the administration of any of the research procedures) and 'unexpected'

(not in our list of expected events), and also occurred within 24h of the study assessment, these will be reported to the lead and local in-country ethics committees, sponsor, UoB team and UoB ethics committee (appendix 4).

Auditing

The study may be subject to inspection and audit by the Chapidze Emergency Cardiology Center, under their remit as sponsor, and other regulatory bodies, to ensure adherence to agreed and relevant principles of GCP and local regulatory frameworks.

Research sites will receive study-specific training before recruitment commences, and all sites will be monitored by the research team throughout the study period.

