In-patient hospitalisation of existing hospitalisation Persistent or significant				Cause of death: Initial Prolonged Date of	
In-patient hospitalisation of existing hospitalisation Persistent or significant disability/incapacity				Cause of death: Initial Prolonged Date of	D D M M Y Y Y Y D D M M Y Y Y Y
In-patient hospitalisation of existing hospitalisation Persistent or significant				Cause of death: Initial Prolonged Date of	

Date of Onset	D D M M	Y Y Y Y	Date became serious	D D M M Y Y Y
Date aware	D D M M	Y Y Y Y	Date resolved	D D M M Y Y Y Y
			or tick if ongoing	
	Causality Assse	ssment (perfo	rmed by Medica	al Doctor)
Is the event directly relat	ed, or caused			
by participation in this stu	udy?			
Yes No No				
Person reporting				
Name				Date reported
Signature of Lead Doctor medically qualified delega				D D M M Y Y Y
 Send this even Enter this fo 	([name] or Ta	within 2 workin [name]	_
NAME OF PERSON ENTERIN	IG THIS FORM ON 1	THE DATABASE:		
DATE FORM WAS ENTERED	D D M M	Y Y Y Y]	

Part 2:

To be completed by the Main Coordinating

Centre Chief Investigator

On receipt of an SAE Form, a unique SAE number will be issued. The CI or delegate will independently determine the seriousness, relatedness and the expectedness of the SAE. An SAE judged by the PI, CI or delegate to have a reasonable causal relationship with the study will be regarded as a related SAE. The causality assessment given by the PI will not be downgraded by the CI or delegate. If the CI or delegate disagrees with the PI's causality assessment, the opinion of both parties will be documented, and where the event requires further reporting, the opinion will be provided with the report to Local and UoB Ethics Committees, the Sponsor and the UoB Breathe Well Team, within 15 days of receipt.

Initial Report

Unique SAE number

Review of relatedness to the study by Chief Investigator or delegate

Relateness to study

If the event is related, fill in the Expectedness section, below.

If the event is not related, do not do not assess expectedness, and do not report the event.

Signature of CI or delegate

Is the event expected, according to the protocol?

Expected

See list at end of this form

Related

Date of CI or delegate signature

Unrelated

If event is related and unexpected, please report it to:

Name of Chief Investigator

or delegate

1) Local Ethics 2) UoB team 3) The Sponsor

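### The Harms section and Appendix 4 conflict on which SAEs are notified externally: only the former adds a 24-hour window tied to study assessments, which leaves out nearly all PR sessions

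*Protocol*

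**What the plan says.** The serious adverse events text under Harms sets two levels of reporting.

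- **Internal.** Every SAE is recorded, and "SAEs will be reported to the chief investigator immediately and within 2 working days of being made aware of the event". No time window applies.
- **External.** The event must be related ("resulted from the administration of any of the research procedures"), unexpected, "and also occurred within 24h of the study assessment, these will be reported to the lead and local in-country ethics committees". The sponsor, the UoB team and the UoB ethics committee complete the list of recipients. The sentence ends by citing Appendix 4.

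Appendix 4, Part 2 of the SAE form, has no window. An event that is related and "unexpected, please report it to" local ethics, the UoB team and the sponsor. The expectedness table that follows repeats this for any serious event not on its list.

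The Data collection methods section uses Study assessment 1, 2 and 3 as headings for the baseline, end-of-programme and 6-month visits. Of the second it says "At the end of the PR programme, participants will be invited to a second study assessment", which places that visit after the programme. Exercise sessions are called PR sessions throughout.

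On where the risk lies, the Harms section states: "There are some potential SAEs which could be expected to occur during the exercise components of the PR programme".

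**The concern.** The three conditions in the Harms text are joint, so failing any one stops external notification. The time condition is anchored to the research visits, while the same section places the potential SAEs in the exercise programme. An SAE in mid-programme that the doctor judges to be caused by the exercise, and that is not on the expected list, fails the condition on timing alone.

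Appendix 4 would send that same event onward. Nothing in the protocol says which text prevails, so what happens depends on which page staff follow. At stake is formal notification of independent bodies about related, unexpected harm from a programme that the protocol says is not yet offered in Georgia. The Study Steering Committee meets only every 6 to 12 months, so it is not a prompt substitute.

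**Working it through.** The plan gives no figure to reproduce. The check is a comparison of the two rules, followed by simple arithmetic on what the window covers.

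**1. One event under both rules.** Take a related, unexpected SAE during a PR session in week 4.

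| Step | Harms section | Appendix 4 |
|---|---|---|
| Recorded and sent to chief investigator | Yes | Yes |
| Related | Met | Met |
| Unexpected | Met | Met |
| Within 24 h of a study assessment | Not met | Not required |
| Notified to ethics, sponsor and UoB team | No | Yes |

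**2. Could study assessment include a PR session?** The term heads three research visits, and no section applies it to a PR session. If it were stretched that far, a 24-hour limit would still stand in one text and not in the other, so the conflict would remain.

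**3. Share of follow-up covered.** Inputs: three study assessments, a 24 h window (Harms section), and 6 months taken as 183 days.

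- Window after each visit: 3 × 1 day = 3 days; 3 / 183 = 1.6%.
- Window before and after each visit: 3 × 2 days = 6 days; 6 / 183 = 3.3%.
- If the one-to-one pre-rehabilitation assessment is a separate visit and also counts: 4 / 183 = 2.2%, or 8 / 183 = 4.4% both ways.

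**4. Share of the programme covered.** The Outcome measures section gives 6 to 8 weeks, that is 42 to 56 days. The 24 h after baseline covers 1 day: 1 / 42 = 2.4% to 1 / 56 = 1.8%. A two-sided window adds at most the day before the end-of-programme visit: 2 / 42 = 4.8% to 2 / 56 = 3.6%.

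**5. Number of sessions concerned.** Session frequency is left to Phase 1, so this is an assumed range. Appendix 1 raises once or twice a week; the background cites exercise two to three times a week. For 30 intervention participants:

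- low: 1 per week × 6 weeks × 30 = 180 participant-sessions;
- high: 3 per week × 8 weeks × 30 = 720 participant-sessions.

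Nearly all of these would fall outside the window.

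**6. Recipients.** The lists also differ. The Harms text names lead and local in-country ethics committees, the sponsor, the UoB team and the UoB ethics committee. The narrative in Part 2 of the form names local and UoB ethics committees, the sponsor and the UoB team. The action list in Part 2 names local ethics, the UoB team and the sponsor. The expectedness table says only ethics, sponsor and UoB team.

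**The case against.** The strongest reply is that practice would follow the form. The Harms sentence cites Appendix 4, staff complete that form for each SAE, and the form has no window. A reader might infer that these events would certainly never reach ethics or the sponsor; the documents do not support that. This point stands, and it is why the finding is a conflict with an indeterminate outcome.

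A reader might also infer that oversight would lose sight of such events altogether. That goes too far. All SAEs go to the chief investigator whatever their timing. The SAE form is entered on the database, to which UoB collaborators have restricted access, and the sponsor is itself the main recruiting centre. What may be lost is formal external notification.

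Three further points stand in part.

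- Appendix 4 lists several cardiac conditions and musculoskeletal problems as expected and not to be reported. Many foreseeable PR-session events would therefore stay internal with or without the 24-hour clause, which reduces its marginal effect.
- The Harms section says that "physiological and questionnaire-based measures pose no risk to the participants", which tempts one to call the window pointless. But the study assessments include a shuttle walking test, done twice at baseline, so a reporting rule around them has a purpose. The fault is that the window stops there.
- Programme safety is not among the listed feasibility outcomes; only selected non-serious events are said to form part of the study outcomes. The case for change does not need safety to be a key output.

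None of this removes the contradiction.

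**Conclusion.** The point holds as an internal contradiction on external SAE reporting, and it should be corrected. Read as written, the Harms section withholds formal notification of related, unexpected SAEs from nearly all PR sessions and home exercise; Appendix 4 does not. A session that happens to fall within 24 h of an assessment would be covered by both.

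The window covers about 1.6% of a 6-month follow-up, or about 3.3% if two-sided. These are shares of calendar time. Neither they nor the 180 to 720 participant-sessions should be read as an estimate of missed events: the protocol gives no SAE rate and says it does not anticipate any. The conclusion rests on reading study assessment as the three headed visits, which is the only use the protocol makes of the term. The session range rests on a frequency not yet fixed.

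**What to change.** Reconcile the two texts in one amendment.

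1. Delete the 24-hour clause from the external reporting sentence in the Harms section, so that its conditions are those of Appendix 4: related and unexpected.
2. State that the rule applies to every related and unexpected SAE from consent to the 6-month assessment, including those arising in PR sessions, home exercise and study assessments. The words related and unexpected should be kept, since both texts limit external reporting to such events.
3. Use one recipient list in the Harms section, the Part 2 narrative, the Part 2 action list and the expectedness table. Deleting the clause alone would leave these lists in disagreement.

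The cost is a short protocol amendment with matching edits to the form. The downside is possibly a few more SAE reports, in a trial of 60 participants.

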Appendix 4 Serious adverse event guidance and form

Guidance						
How to use this form to report a serious adverse event						
	Definitions					
elated Event An event which directly resulted from any of the study procedures.						
Serious Adverse Event (SAE)	An untoward occurrence that: Results in death Is life-threatening Requires hospitalisation or prolongation of existing hospitalisation*					
	Results in persistent or significant disability or incapacity Or is otherwise considered medically significant by the Study Doctor or CI *Hospitalisation for elective procedures are not regarded as a SAE.					
RELATED Category	Definition	Causality				
Definitely Probably	There is clear evidence to suggest a causal relationship, and other possible contributing factors can be ruled out There is evidence to suggest a causal relationship, and the influence of other factors is unlikely	Related				
Possibly	There is some evidence to suggest a causal relationship. However, the influence of other factors may have contributed to the event (e.g. the patient's clinical condition, other concomitant events or medication)					
Unlikely	There is little evidence to suggest there is a causal relationship. There is another reasonable explanation for the event (e.g. the patient's clinical condition, other concomitant events or medication)	Unrelated				
Not related	Not related There is no evidence of any causal relationship					
If the event is not ser	ious, do not report it.					
Part 1- to be filled ou by the site Medical December	t by clinic site team. The diagnosis and decision of event being directly related, or not to the study activ octor	rity, to be performed				
Have the Medical Doo	ctor at site decide if the event is directly related to the study					
Enter the form on the	e database.					
Send the form to the Central Coordinating office- they fill in Part 2.						

Serious adverse event form

Part 1: To be completed at the patient clinic sites					
Study Name:					
Clinic Name:			Name	e of Lead Doctor	
Participant Details					
Participant ID Number:			Participant Sex:		Male Female
Participant Initials:			Partion Birth:	ipant Date of	D D M M Y Y Y
Event Diagnosis-					
Event Information,					
Describe what happened					
		Yes	No		Details
Death				Date of death:	D D M M Y Y Y
Death				Date of death: Cause of death:	D D M M Y Y Y Y
Death					D D M M Y Y Y Y
In-patient hospitalisation					
				Cause of death:	
In-patient hospitalisation				Cause of death:	
In-patient hospitalisation of existing hospitalisation Persistent or significant				Cause of death: Initial Prolonged Date of	
In-patient hospitalisation of existing hospitalisation Persistent or significant disability/incapacity				Cause of death: Initial Prolonged Date of	D D M M Y Y Y Y D D M M Y Y Y Y
In-patient hospitalisation of existing hospitalisation Persistent or significant				Cause of death: Initial Prolonged Date of	

Date of Onset	D D M M	Y Y Y Y	Date became serious	D D M M Y Y Y
Date aware	D D M M	Y Y Y Y	Date resolved	D D M M Y Y Y Y
			or tick if ongoing	
	Causality Assse	ssment (perfo	rmed by Medica	al Doctor)
Is the event directly relat	ed, or caused			
by participation in this stu	udy?			
Yes No No				
Person reporting				
Name				Date reported
Signature of Lead Doctor medically qualified delega				D D M M Y Y Y
 Send this even Enter this fo 	([name] or Ta	within 2 workin [name]	_
NAME OF PERSON ENTERIN	IG THIS FORM ON 1	THE DATABASE:		
DATE FORM WAS ENTERED	D D M M	Y Y Y Y]	

Part 2:

To be completed by the Main Coordinating

Centre Chief Investigator

On receipt of an SAE Form, a unique SAE number will be issued. The CI or delegate will independently determine the seriousness, relatedness and the expectedness of the SAE. An SAE judged by the PI, CI or delegate to have a reasonable causal relationship with the study will be regarded as a related SAE. The causality assessment given by the PI will not be downgraded by the CI or delegate. If the CI or delegate disagrees with the PI's causality assessment, the opinion of both parties will be documented, and where the event requires further reporting, the opinion will be provided with the report to Local and UoB Ethics Committees, the Sponsor and the UoB Breathe Well Team, within 15 days of receipt.

Initial Report

Unique SAE number

Review of relatedness to the study by Chief Investigator or delegate

Relateness to study

If the event is related, fill in the Expectedness section, below.

If the event is not related, do not do not assess expectedness, and do not report the event.

Signature of CI or delegate

Is the event expected, according to the protocol?

Expected

See list at end of this form

Related

Date of CI or delegate signature

Unrelated

If event is related and unexpected, please report it to:

Name of Chief Investigator

or delegate

1) Local Ethics 2) UoB team 3) The Sponsor

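### The protocol sets conflicting thresholds for calling an SAE related, so a possibly related event may be under-called at site and two reporting safeguards are weakened

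*Protocol*

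**What the plan says.** Five places in the protocol bear on when a serious adverse event (SAE) is related.

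- **Appendix 4, definitions.** A related event is "An event which directly resulted from any of the study procedures". The adverb is underlined in the document.
- **Appendix 4, Part 1 instructions and form.** The site team is told: "The diagnosis and decision of event being directly related, or not to the study activ" (the last word is cut in extraction). A further line has the site's medical do"ctor at site decide if the event is directly related to the study". The Part 1 causality item opens "Is the event directly relat" (also cut), adds causation by participation as an alternative, and offers Yes or No.
- **Appendix 4, causality scale.** There are five grades: Definitely, Probably, Possibly, Unlikely, Not related. Possibly reads: "There is some evidence to suggest a causal relationship. However, the influence of other factors may have contributed to the event". The Unrelated label first appears at Unlikely, whose text begins "There is little evidence to suggest there is a causal relationship".
- **Appendix 4, Part 2.** "An SAE judged by the PI, CI or delegate to have a reasonable causal relationship with the study will be regarded as a related SAE".
- **Protocol body, Serious adverse events.** Related means that the event resulted from the research procedures, with no requirement of directness. The opinion of the local doctor or of the chief investigator is enough. Onward reporting also requires that the event be unexpected and fall within 24 hours of the study assessment.

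**The concern.** These are different standards for one decision, and nothing says which prevails. An event with some evidence of causation and another plausible contributor is described by the Possibly grade, yet it is hard to call direct. Such events are foreseeable here, because the protocol itself describes participants as having comorbidities while doing an exercise intervention.

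At stake is the site doctor's causality opinion, on which two safeguards rest: the either-opinion rule in the body and the rule in Part 2 that the PI's assessment is not downgraded. Both work only when the site has said Yes. In addition, neither Part 1 (Yes/No) nor Part 2 (Related/Unrelated), as extracted, has a field for the five-grade scale, so the site doctor's grade at the time of the event is not kept.

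**Working it through.** No arithmetic reproduces or refutes this point. The check sets the passages side by side and follows the form through.

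**1. The thresholds**

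| Place | Applied by | Standard |
|---|---|---|
| Appendix 4 definition | anyone using the form | directly resulted |
| Part 1 instructions and item | site doctor | directly related, or caused by participation |
| Causality scale | not stated | Unrelated from Unlikely downwards; Possibly appears to be Related |
| Part 2 | PI, chief investigator or delegate | reasonable causal relationship |
| Protocol body | local doctor or chief investigator | resulted from research procedures |

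Definitely and Probably should pass under any row, and Unlikely and Not related should fail. The rows part at Possibly, one grade of five.

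**2. A test case.** Suppose a participant is admitted with a respiratory event within 24 hours of the shuttle walk at a study assessment, with COPD itself a possible contributor. It is not on the expected list at the end of Appendix 4 (angina pectoris, recent myocardial infarction, severe pulmonary hypertension, congestive heart failure, musculoskeletal problems), and it meets the 24-hour condition. Relatedness alone then decides whether the ethics committees and sponsor are told. The scale points to Related; the directness wording points to No.

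**3. What a site No does.** It does not stop the form. The body has all SAEs recorded in the CRF and database and notified to the chief investigator within two working days. Appendix 4 sends the form to the coordinating office without reference to the site's answer. The chief investigator or delegate then judges relatedness afresh. The only site-level instruction not to report concerns non-serious events.

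**4. What a site No costs.** Take the site's *PI* in Part 2 to be the doctor who answers Part 1 (an assumption; the form uses several titles). The four combinations are:

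| Site | Chief investigator | Outcome |
|---|---|---|
| Yes | Related | related |
| Yes | Unrelated | related: no downgrade, both opinions documented |
| No | Related | related |
| No | Unrelated | Part 2: do not report |

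Three of the four end as related. With the site's answer at No, two combinations remain and one of them does. These are counts of routes, not probabilities. The remaining route is exposed to the same wording, because the directness definition heads the guidance for the whole form.

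**5. Size.** The documents give no SAE rate, so the number of affected events cannot be estimated. The planned sample is 30 per arm, so one reclassified participant is 1/30 = 3.3% of an arm.

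**The case against.** The strongest reply is that the form has a second line of defence. Every SAE reaches the chief investigator, who judges it independently, may raise the site's assessment and may not lower it. That stands, and it rules out several stronger readings.

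- A reader might infer that possibly related events are filtered out at site. They are not: no site answer holds the form back, and the instruction not to report unrelated events sits in Part 2, after central review.
- A reader might infer that the chief investigator sees only a No. Part 1 also carries the diagnosis, a description of what happened, the seriousness criteria and several dates.
- A reader might infer that the count of related SAEs could never be rebuilt. The narratives are kept, so events can be re-adjudicated; what is lost is the site doctor's grade at the time.
- A reader might infer that the commonest exercise-related SAEs are removed. No figure in the protocol supports that.

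Three further points have weight. The Part 1 item's second limb, causation by participation, is not qualified by directness, so a doctor could still answer Yes; but the answer then depends on the reader. The Yes/No box can be read as recording the scale's Related/Unrelated column, though the form does not say so. And the Possibly row's label is inferred from a table broken in extraction. The conflict survives without that row, since the directness wording, Part 2 and the body differ anyway. Finally, the number of related SAEs is not a listed outcome, so this is a matter of safety reporting rather than of the trial's results.

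**Conclusion.** The protocol contradicts itself on when an SAE is related, and the contradiction should be removed. The supported consequence is limited: a possibly related event may be under-called at site, which leaves the either-opinion and no-downgrade safeguards with nothing to act on, and the chief investigator may then apply the same directness definition and close the event as not reportable. The disagreement affects one grade of five. Its frequency is unknown, and neither the sample size nor the planned analysis changes.

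This rests on two assumptions: that Possibly falls under Related, as the row order suggests, and that the PI in Part 2 is the doctor answering Part 1. The expected-event list and the 24-hour condition are separate limits on onward reporting and are not part of this point.

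**What to change.** - Use one definition of relatedness in the protocol body (Serious adverse events), the Appendix 4 guidance, Part 1 and Part 2, and remove the word *directly* from the definition, the Part 1 instructions and the Part 1 item.
- State once which of the printed grades count as Related. The layout suggests Definitely, Probably and Possibly; confirm this against the unbroken table.
- Replace the bare Yes/No in Part 1 with the five grades already printed in the guidance, so that the site's judgement is on record when the chief investigator reviews it.

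The cost is a wording edit and one database field. The small downside is that a few more SAEs may be classed as related.
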